### 7.5 BMX-001

It is well-established that induction of oxidative stress after RT and chemotherapy plays a major role in tumor and normal tissue therapy responses [38,39]. Ironically, the responses in tumor tend to protect vascular endothelium and tumor cells from RT damage [40], whereas these same stresses after RT promote normal tissue damage [38,41]. A variety of approaches have been investigated to mitigate oxidative stress post irradiation, including the free radical scavenger, amifostine [42-44]. Although this agent is approved for this use, its daily use is limited by side effects [42,44]. Other agents that have been tested pre-clinically and clinically include nitroxides and genistein, but these are not currently approved for protection against normal tissue injury post irradiation, and neither provides catalytic inactivation of reactive species responsible for oxidative stress [42]. Over the past 20 years, [name] and colleagues have developed a class of manganese (Mn) porphyrin-based compounds that: 1) are potent anti-inflammatory agents and 2) catalytically inactivate a range of reactive oxygen species, including peroxynitrite and superoxide anion [45-47]. These properties give this class of compound the unique function of protecting normal tissues while also augmenting tumor killing in patients undergoing radiation and chemotherapy. In addition to inactivation of reactive oxygen species, these drugs inhibit transcriptional activity of stress-induced transcription pathways by either eliminating reactive oxygen species that activate stress responses or by indirectly preventing activation. Transcription factors known to be inhibited by this class of metalloporphyrin include HIF-1 [48,49], NFkB [50], SP-1 [51] and AP-1 [45]. The most recently developed compound, BMX-001 (MnTnBuOE-2-PyP5+), is among the most highly potent in a series of well over two dozen metalloporphyrins that have been evaluated thus far [52]. BMX-001 is lipophilic and crosses the blood brain barrier. This drug has been licensed for commercial development and will be the lead compound for this project.

In normal brain, oxidative stress incites inflammatory responses that contribute to white matter degradation and cognitive deficits. Metalloporphyrins have been shown to protect against a range of CNS conditions associated with inflammation, including stroke [53] and spinal cord damage [54-56]. Furthermore, metalloporphyrins have been shown to protect mice from total body irradiation toxicity [57] and xerostomia following parotid gland irradiation [58]. Radiation-induced lung injury was protected against by administration of metalloporphyrins in rhesus macaques [59]. Relevant to this application, Weitzel and colleagues showed protection against hippocampal stem cell loss and white matter degradation after whole brain RT therapy [58]. In this study, C57BL/6J mice were exposed to 8 Gy of whole brain irradiation with and without concurrent BMX-001. In mice that had been treated with BMX-001 and RT, there was preservation of myelin in the corpus callosum and anterior commissure in comparison to mice that received only RT without BMX-001. Moreover, the mice that received BMX-001 and RT performed better on rotorod tests and running wheel tests, both tests of cognitive function, in comparison to the RT alone group. It is well-established that oxidative stress and cognitive losses are a consequence of brain irradiation [6]. Therefore, there is ample evidence to suggest that BMX-001 will reduce the magnitude of oxidative stress after RT therapy and TMZ; this will lead to protection against cognitive losses and improvement in HRQoL.

In tumors, [name] and colleagues showed that RT and chemotherapy increase oxidative stress, driving upregulation of HIF-1 [40,60], a transcription factor that promotes endothelial and tumor cell survival and increases tumor aggressiveness [61]. Radiation creates persistent oxidative stress in surviving cells, which upregulates NFkB [62]; this transcription factor also drives treatment resistance [63]. Treatment with this new class of metalloporphyrin prevents HIF-1 and NFkB upregulation in tumors after RT and chemotherapy and improves tumor treatment responses [57]. Using LN-18 and LN-229 HGG cell lines, BMX-001 showed no significant protective effect on clonogenic survival when

cells were also exposed to RT [64]. The effect of BMX-001 has been studied on mouse flank HGG xenografts. In this study by Weitzel and colleagues, while RT did lead to a reduction in GBM tumor growth in comparison to saline alone, the combination of BMX-001 and RT demonstrated a greater and significant degree of tumor reduction [64]. This demonstrated that BMX-001 has a differing effect in tumor tissue in comparison to normal tissues with BMX-001 showing potential to protect normal tissues and sensitize tumors to RT. Thus, the rationale for this protocol is based on the demonstrated dual activity of BMX-001 to protect normal tissue while sensitizing tumors to therapy.

## 7.6 Study Rationale

BMX-001 added to RT and TMZ has the potential not only to enhance the survival of HGG patients but also to protect against deterioration of cognition, impairment of HRQoL, and bone marrow suppression. We have performed a Phase 1 trial of BMX-001 at escalating doses in combination with standard RT, 33 fractions to 59-60 Gy, plus daily TMZ at the standard dosing of 75 mg/m^2. We have confirmed that BMX-001, when added to standard RT and TMZ, will be safe at pharmacologically relevant doses in patients with newly diagnosed HGG. Safety and MTD have been determined in the Phase 1 portion of this study, thus we will now move to a Phase 2 study comparing concurrent daily TMZ and standard RT alone to the same regimen in combination with BMX-001 to assess the impact of BMX-001 on the survival of newly diagnosed HGG patients. We hypothesize that BMX-001, when added to standard RT and TMZ, will be safe and will sensitize the malignancy resulting in enhanced patient survival. In addition, BMX-001 will protect normal brain tissue from the effects of radiation and chemotherapy and will protect bone marrow from chemotherapy-induced thrombocytopenia.

# **8 OBJECTIVES AND ENDPOINTS**

	Objective	Endpoint	Analysis
Primary	To determine the maximum tolerated dose (MTD) of BMX-001 in combination with standard RT and TMZ in newly diagnosed HGG patients	MTD is defined as the dose level that has an estimated DLT rate nearest to 0.25	See Section 16.4.1
Secondary	To assess the safety and tolerability of BMX-001 in combination with standard RT and TMZ in newly diagnosed HGG patients	Proportion of patients with DLT	See Section 16.4.1.4
Secondary	To examine the impact on cognition of BMX-001 in combination with standard RT and TMZ in treatment of newly diagnosed HGG patients	Mean change between baseline and week 24 in normalized scores for cognition using standardized cognitive tests and computerized battery CNS Vital Signs ® . This includes Hopkins Verbal Learning Test-Revised, Trails Making Test Parts A and B, and Controlled Word Association Test and CNS Vital Signs ® battery consisting of seven tests that measure verbal and visual memory, finger tapping, symbol digit coding, the Stroop Test, a test of shifting attention, and continuous performance test.	See Section 16.4.1.4
Secondary	To assess the efficacy of BMX-001 in combination with standard RT and TMZ in newly diagnosed HGG patients based upon overall survival (OS) and progression free survival (PFS)	Median OS, where OS is defined as the time to death from the time of protocol treatment is initiated Median PFS, where PFS is defined as the time between initiation of protocol treatment and the first recurrence of disease or death	See Section 16.4.1.4
Secondary	To describe radiographic response in newly diagnosed HGG patients treated with BMX-001 in combination with standard RT and TMZ	Proportion of patients with radiographic response	See Section 16.4.1.4
Secondary	To characterize the pharmacokinetic profile of BMX-001 when delivered in combination with RT and TMZ in newly diagnosed HGG patients	Plasma concentrations and calculated pharmacokinetic parameters (maximum concentration, time to reach maximum concentration, area under the curve, half-life, total body clearance, and volume of distribution) will be determine for BMX-001	See Section 19.1
Exploratory	To describe patient-reported outcomes of HRQoL in newly diagnosed HGG patients treated with BMX-001 in combination with standard RT and TMZ	Mean change from baseline at each follow-up assessment for subscales of the following PROs include Functional Assessment of Cancer Therapy-Brain Cancer (FACT-BR) version 4, Functional Assessment of Cancer Therapy- Fatigue (FACIT-Fatigue) subscale, version 4, Functional Assessment of Cancer Therapy- Cognition (FACT-Cog) subscale, Beck depression inventory (BDI-II), revised version, Godin Leisure questionnaire	See Section 16.4.1.5
Exploratory	To describe changes in hair loss during BMX-001 in combination with standard RT and TMZ in newly diagnosed HGG patients	Subjective investigator and patient assessment, photographs	See Section 16.4.1.5

### **Table 1: Phase 1 Objectives and Endpoints**

### Table 2: Phase 2 Objectives and Endpoints

	Objective	Endpoint	Analysis
Primary	To assess the efficacy of standard RT and TMZ in combination with BMX- 001 compared to standard RT and TMZ alone in newly diagnosed HGG patients based upon overall survival (OS).	Median OS, where OS is defined as the time to death from randomization.	See Section 16.5.1
Secondary	To examine the impact on cognition of BMX-001 in combination with standard RT and TMZ in treatment of newly diagnosed HGG patients.	Mean change between baseline and week 24 in normalized scores for cognition using standardized cognitive tests and BAC This includes Hopkins Verbal Learning Test-Revised, Trails Making Test Parts A and B, and Controlled Word Association Test and BAC (VeraSci) consisting of seven tests that measure verbal memory and learning, working memory, motor function, verbal fluency, speed of processing, and executive function.	See Section 16.5.2
Secondary	To assess protection of bone marrow against chemotherapy induced thrombocytopenia in patients being treated with standard RT and TMZ in combination with BMX-001 compared to standard RT and TMZ alone in newly diagnosed HGG patients.	Proportion of patients with thrombocytopenia grade 3 or 4 adverse event during standard RT and TMZ treatment. Proportion of patients with a platelet count below 100,00 during standard RT and TMZ treatment and who had suspension of TMZ therapy.	See Section 16.5.2.2
Secondary	To assess the safety and tolerability of standard RT and TMZ in combination with BMX-001 compared to standard RT and TMZ alone in newly diagnosed HGG patients.	Proportion of subjects who experience grade 3 or 4 adverse event during standard RT and TMZ treatment. Proportion of subjects who experience grade 3 or 4 adverse event that are definitely, possibly, or probably related to BMX-001 treatment.	See Section 16.5.2
Secondary	To assess the efficacy of standard RT and TMZ in combination with BMX- 001 compared to standard RT and TMZ alone in newly diagnosed HGG patients based upon progression-free survival (PFS).	Median PFS, where PFS is defined as the time between initiation of protocol treatment and the first recurrence of disease or death.	See Section 16.5.2
Secondary	To assess radiographic response in newly diagnosed HGG patients treated with standard RT and TMZ in combination with BMX-001 compared to standard RT and TMZ alone.	Proportion of subjects with complete or partial radiographic response.	See Section 16.5.2
Secondary	To characterize the repeated-dose pharmacokinetic profile of BMX-001 when delivered in combination with RT and TMZ in newly diagnosed HGG patients.	Plasma concentrations and calculated pharmacokinetic parameters (maximum concentration, time to reach maximum concentration, area under the curve, half-life, total body clearance, and volume of distribution) will be determined for BMX-001.	See Section 16.5.2
Exploratory	To describe patient-reported outcomes of HRQoL in newly diagnosed HGG patients treated with standard RT and TMZ in combination with BMX-001 compared to standard RT and TMZ alone.	Mean change from baseline at each follow-up assessment for subscales of the following PROs include Functional Assessment of Cancer Therapy-Brain Cancer (FACT-BR) version 4, Functional Assessment of Cancer Therapy- Fatigue (FACIT-Fatigue) subscale, version 4, Functional Assessment of Cancer Therapy- Cognition (FACT-Cog) subscale, Beck depression inventory (BDI-II), revised version, Godin Leisure questionnaire.	See Section 16.5.3

Exploratory	To describe changes in hair loss in newly diagnosed HGG patients treated with standard RT and TMZ in combination with BMX-001 compared to standard RT and TMZ alone.	Subjective investigator and patient assessment, photographs.	See Section 16.5.3
Exploratory	To describe change in white matter integrity in newly diagnosed HGG patients treated with standard RT and TMZ in combination with BMX- 001 compared to standard RT and TMZ alone.	MRI Brain Diffusion Tensor /Susceptibility Imaging (white matter integrity).	See Section 16.5.3

# 9 INVESTIGATIONAL PLAN

### 9.1 Study Design

As this study is a Phase 1/2 study, this protocol includes a Phase 1 Dose Escalation portion and a randomized Phase 2 portion. In the Phase 1 Dose Escalation portion of the study, the dose of BMX-001 will be escalated, while the dose of daily TMZ and RT (chemoradiation phase) will remain fixed and will be followed by adjuvant TMZ (adjuvant phase). The randomized Phase 2 study component will assess the impact of BMX-001 in combination with daily TMZ and standard RT in comparison to daily TMZ and standard RT in newly diagnosed HGG patients on overall survival and, as secondary endpoints, impact on cognition and on bone marrow suppression.

A clinical research coordinator will schedule all of the appointments and the calendar will be provided to the patients. For study schema, please see Section 6 and Figure 1.

### 9.1.1 Phase 1 Specific Design

This Phase 1 study will be a single-site study of escalating doses of BMX-001 in combination with RT and TMZ (chemoradiation phase), followed by adjuvant TMZ (adjuvant phase). In the chemoradiation phase, external beam RT therapy will be given over less than seven weeks in 30-33 fractions for a total dose of 59-60 Gy. TMZ (75 mg/m^2 po daily) will be started on the first day of RT and will be administered for 42 days. TMZ will be given before RT daily. In line with Brain Tumor Center standard of care, adjuvant TMZ therapy will begin 2 to 4 weeks after the completion of RT. Adjuvant TMZ could be administered for up to 12 scheduled 28-day cycles. TMZ will be given orally at night on days 1-5 of 28-day cycle. During the chemoradiation phase and 2 weeks thereafter, CBC with differential and a CMP will be obtained weekly. A minimum of 3 subjects and a maximum of 18 subjects with newly diagnosed HGG who are patients at The Preston Robert Tisch Brain Tumor Center clinic at Duke University Medical Center will be enrolled into this study during a 12-month period. We will aim to enroll 3 subjects every eight to ten weeks. Once 3 patients have undergone treatment without experiencing a DLT after a monitoring period of four weeks following completion of all doses of BMX-001, the dose of the subsequent group of 3 patients will be escalated.

### 9.1.1.1 Dose Escalation for BMX-001 in Phase 1

BMX-001 will be administered subcutaneously as a loading dose before starting concurrent chemoradiation (days -5 through 0 depending on patient/radiotherapy scheduling). After the loading dose, the dose levels will be given two times per week for 8 weeks. The starting dose level will be 7 mg loading dose. BMX-001 dose escalation will be 7 mg loading dose, 14 mg loading dose, 28 mg loading dose, and 42 mg loading dose in four dose levels. After the loading dose, the BMX-001 dose will be administered at the amounts listed below twice a week (see Table 3 below). The corresponding volumes of BMX-001, Injection Solution 10 mg/mL associated with the loading dose are as follows (the equivalent dose for a 70 kg adult is also given):

0.7 mL/subject loading dose = 7 mg/subject and is equivalent to 0.1 mg/kg for 70 kg subject 1.4 mL/subject loading dose = 14 mg/subject and is equivalent to 0.2 mg/kg for 70 kg subject 2.8 mL/subject loading dose = 28 mg/subject and is equivalent to 0.4 mg/kg for 70 kg subject 4.2 mL/subject loading dose = 42 mg/subject and is equivalent to 0.6 mg/kg for 70 kg subject

The corresponding maintenance doses would be equivalent to the following:

0.35 mL/subject dose = 3.5 mg/subject and is equivalent to 0.05 mg/kg for 70 kg subject 0.7 mL/subject dose = 7 mg/subject and is equivalent to 0.1 mg/kg for 70 kg subject 1.4 mL/subject dose = 14 mg/subject and is equivalent to 0.2 mg/kg for 70 kg subject 2 mL/subject dose = 20 mg/subject and is equivalent to 0.3 mg/kg for 70 kg subject BMX-001 will be administered by subcutaneous injection of a sterile 10 mg/mL solution in saline. Syringes will be either 1 mL or 3 mL with a 25 gauge X 5/8 inch needle depending on the volume of injection. The subcutaneous injections may be at any optimum site on the torso, the upper leg or upper arm. Sites of injection should be alternated. Subsequent (maintenance) doses will be one-half the size of the loading dose (except Group IV where the subsequent dose is rounded down to 20 mg) and should be administered twice weekly. The first dose should be delivered 3 to 5 days after the loading dose and further doses delivered at 3 to 4 day intervals to average 2 doses per week. The BMX-001 doses other than the loading dose will be delivered within 12 hours before or after RT. Schedule of subsequent doses will be dependent on the day of the loading dose and radiation schedule. For each week the doses are given, the days will either be Monday and Thursday for injections or Tuesday and Friday for injections. BMX-001 will not be administered on Saturday or Sunday.

	Subject Group			
	I	I	III	IV
		Loading	g Dose 	
	7 mg	14 mg	28 mg	42 mg
Week	Subsequent Doses 			
1	3.5 mg b.i.w.	7 mg b.i.w.	14 mg b.i.w.	20 mg b.i.w.
2	3.5 mg b.i.w.	7 mg b.i.w.	14 mg b.i.w.	20 mg b.i.w.
3	3.5 mg b.i.w.	7 mg b.i.w.	14 mg b.i.w.	20 mg b.i.w.
4	3.5 mg b.i.w.	7 mg b.i.w.	14 mg b.i.w.	20 mg b.i.w.
5	3.5 mg b.i.w.	7 mg b.i.w.	14 mg b.i.w.	20 mg b.i.w.
6	3.5 mg b.i.w.	7 mg b.i.w.	14 mg b.i.w.	20 mg b.i.w.
7	3.5 mg b.i.w.	7 mg b.i.w.	14 mg b.i.w.	20 mg b.i.w.
8	3.5 mg b.i.w.	7 mg b.i.w.	14 mg b.i.w.	20 mg b.i.w.
 Dose of BMX-001 for Injection, 10 mg/mL administered to subject.				

Table 3: Loading Doses and Subsequent Doses for BMX-001 in Phase 1 Study

#### 9.1.1.2 Definition of Dose-Limiting Toxicity (DLT)

Toxicities will be graded according to the NCI CTCAE version 4.03 criteria. DLTs will be defined as any of the following events that are possibly, probably, or definitely attributable to BMX-001 during dose escalation.

A dose limiting toxicity is defined as an adverse event or laboratory abnormality that is: a. assessed as unrelated to disease progression, intercurrent illness, or concomitant medications; b. occurs during and/or following the first dose of BMX-001; and c. meets any of the following criteria:

### 9.1.1.2.1 Non-hematologic

- The occurrence of non-hematologic grade 3 or greater adverse events considered to be possibly, probably, or definitely related to BMX-001 during treatment with BMX-001, excluding grade ≥ 3 alopecia and elevation in alkaline phosphatase, grade ≥ 3 nausea or vomiting unless occurring despite the use of standard anti-emetics; and grade 3 hypertriglyceridemia or hypercholesterolemia unless occurring despite standard lipidlowering agents.
- 2. > 14 day delay to re-treat due to failure to resolve any grade 3 or greater non-hematologic drug-related toxicity to re-treatment criteria or pre-treatment baseline.
- 3. Grade  $\geq$  2 neurological toxicity that impairs activities of daily living and persists  $\geq$  7 days.
- 4. Inability to complete > 75% of the planned RT treatments.

### 9.1.1.2.2 Hematologic

Occurrence of any of the following hematologic adverse events will be defined as a DLT:

1. Grade 4 neutropenia (ANC, including bands, ≤0.5 x 109 /l);

- 2. Grade 3 thrombocytopenia (platelet count of  $\leq$  50x109/l);
- 3. > 14 day delay to re-treat due to failure to resolve hematologic toxicity to re-treatment criteria.

9.1.1.2.3 Other Considerations Not applicable

#### 9.1.1.3 **Dose Modification**

There are no reductions in the BMX-001. If adverse events occur that require holding BMX-001, the dose will remain the same once treatment resumes.

Any toxicity possibly, probably, or definitely associated with BMX-001 should be managed according to standard medical practice. There is no available antidote for BMX-001.

Subjects should be assessed clinically for toxicity prior to, during, and after each injection. If an unmanageable toxicity, i.e. in the opinion of the subject and treating physician, occurs because of BMX-001 at any time during the study, treatment with BMX-001 should be discontinued.

Injection of BMX-001 should be interrupted for subjects who develop dyspnea or clinically significant hypotension and it may be re-started at the following scheduled injection, if the treating physician considers it safe for the subject to proceed on study. Subjects who experience a Grade 3 or 4 allergic reaction / hypersensitivity, adult respiratory distress syndrome, or bronchospasm (regardless of grade) will be discontinued from BMX-001 treatment.

Regardless of the reason for holding study drug treatment, the maximum allowable length of treatment interruption is 3 weeks. If BMX-001 is held for greater than 3 weeks, BMX-001 will be discontinued.

### 9.1.2 Phase 2 Specific Design

The Phase 2 portion of this study will be a randomized, multi-center study comparing Arms A and B. Arm A will consist of daily TMZ and RT with BMX-001 and Arm B will include daily TMZ and RT alone.

For the Phase 2 Study, BMX-001 will be administered subcutaneously as a loading dose before starting concurrent chemoradiation (days -5 through 0 depending on patient/MRI scheduling), during treatment, and after treatment concludes. After the loading dose, the subsequent doses will be given two times per week for 8 weeks. The BMX-001 doses other than the loading dose will be delivered within 12 hours before or after RT. Patients will be randomized with a treatment arm allocation ratio of 1:1 to receive BMX-001 or to proceed with RT and TMZ alone. There will be 160 patients enrolled in this phase of the study (80 subjects per arm). The Phase 1 trial has confirmed the safe RP2D for BMX-001. The loading dose determined safe from Phase 1 and being studied in Phase 2 is 28 mg/subject and the maintenance doses are each 14 mg/subject.

BMX-001 will be administered by subcutaneous injection of a sterile 10 mg/mL solution in saline. The subcutaneous injections may be at any optimum site on the torso, the upper leg or upper arm. The first subsequent dose should be delivered 1 to 5 days after the loading dose and subsequent doses delivered at 3 to 4 day intervals to average 2 doses per week. The Phase 2 criteria for holding, retreating and discontinuing BMX-001 is captured in Section 13.4 BMX-001 Treatment Criteria.

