# 13.4 BMX-001 Treatment Criteria

If adverse events occur that require holding BMX-001, the dose will remain the same once treatment resumes. Missed doses should be made up at the end of treatment to achieve the total number of planned doses (17).

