#### 13.4.1 Phase 2 - Criteria for holding BMX-001

#### Non-Hematologic Criteria

- The occurrence of non-hematologic grade 3 or greater adverse events considered to be possibly, probably, or definitely related to BMX-001 during treatment with BMX-001, excluding grade ≥ 3 alopecia and elevation in alkaline phosphatase, grade ≥ 3 nausea or vomiting unless occurring despite the use of standard anti-emetics; and grade ≥ 3 hypertriglyceridemia or hypercholesterolemia unless occurring despite standard lipid lowering agents.
- 2. Intolerable  $\geq$  Grade 2 Injection Site Reactions
- 3.  $\geq$  Grade 2 electrocardiogram prolonged QTc interval

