#### 13.4.2 Phase 2- Re-treatment Criteria for BMX-001

Non-Hematologic

- 1. Resolution of any grade 3 or greater toxicity felt to be possibly, probably or definitely attributable to BMX-001 to grade 1 or pre-treatment baseline.
- 2. Resolution of Intolerable  $\geq$  Grade 2 Injection Site Reactions to  $\leq$  Grade 1
- 3. Resolution of Grade 2 electrocardiogram prolonged QTc interval to baseline, or after review by sponsor.

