#### 13.4.3 Phase 2- Discontinuation Criteria for BMX-001

Inability to resolve any grade 3 or greater toxicity felt to be possibly, probably or definitely attributable to BMX-001 to grade 1 or pre-treatment baseline within 21 days.

For both non-hematologic and hematologic events, if any event requires holding BMX-001 > 21 days without retreatment, BMX-001 would not be started again. In these cases, subjects should continue to be followed for survival without the completion of study treatment visits.

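### Section 13.4, the Phase 2 rule set for BMX-001, omits the 9.1.1.3 permanent stops for ARDS and any-grade bronchospasm, so re-challenge after recovery is permitted

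*Protocol*

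**What the plan says.** **Phase 1 rule.** Protocol 9.1.1.3 (Dose Modification) sits under 9.1.1, Phase 1 Specific Design. It treats two groups of events differently. After dyspnea or clinically significant hypotension, dosing is interrupted, and "it may be re-started at the following scheduled injection, if the treating physician considers it safe for the subject to proceed on study". Patients with a grade 3 or 4 "allergic reaction / hypersensitivity, adult respiratory distress syndrome, or bronchospasm (regardless of grade) will be discontinued from BMX-001 treatment".

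**Phase 2 pointer.** Protocol 9.1.2 states: "The Phase 2 criteria for holding, retreating and discontinuing BMX-001 is captured in Section 13.4 BMX-001 Treatment Criteria".

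**Phase 2 rules.**
- 13.4.1 requires a hold for "non-hematologic grade 3 or greater adverse events considered to be possibly, probably, or definitely related to BMX-001", apart from a few listed exclusions. It also covers intolerable injection site reactions and QTc prolongation, both from grade 2.
- 13.4.2 sets the condition for restarting: "Resolution of any grade 3 or greater toxicity felt to be possibly, probably or definitely attributable to BMX-001 to grade 1 or pre-treatment baseline".
- 13.4.3 discontinues for "Inability to resolve any grade 3 or greater toxicity felt to be possibly, probably or definitely attributable to BMX-001" to grade 1 or baseline within 21 days, and for any hold longer than 21 days.
- The opening of 13.4 adds: "If adverse events occur that require holding BMX-001, the dose will remain the same once treatment resumes". It also asks that missed doses be made up, to a total of 17.

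**Other routes.** Protocol 13.5 lists unacceptable toxicity and allergic reactions to BMX-001 among the reasons a subject comes off study, and gives no grade for either. Protocol 13.7.1 lets the investigator withdraw a subject at any time, with adverse events as one listed reason.

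**The concern.** One protocol contains two different rules for the same respiratory events. In 9.1.1.3, ARDS or any bronchospasm ends BMX-001. In 13.4, the section Phase 2 sites are told to use, neither event is named, and the general toxicity rule allows a restart after recovery.

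The stake is patient safety. A site following 13.4 literally could give the drug again, at the same dose, to a patient who has recovered from a serious respiratory reaction. It would also find no written instruction for a milder bronchospasm. Protocol 9.1.1.3 notes that BMX-001 has no antidote.

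**Working it through.** No figure in the plan depends on this, so the check is a comparison of text.

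**Step 1: which section governs Phase 2.** 9.1.1.3 is numbered under the Phase 1 design. 9.1.2 assigns Phase 2 holding, re-treating and discontinuing to 13.4, and the subsections 13.4.1 to 13.4.3 are each labelled Phase 2.

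**Step 2: what was carried over.** Two 9.1.1.3 rules reappear for Phase 2. The same-dose rule is in the opening of 13.4. The three-week limit on interruption is in 13.4.3 (3 x 7 = 21 days) and again in 9.1.5. The permanent stops do not reappear.

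**Step 3: each event under both rules.**

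| Event | 9.1.1.3 | 13.4 | 13.5 |
|---|---|---|---|
| ARDS, related, grade 3+ | Discontinue | Hold; restart allowed at grade 1 or baseline; stop if unresolved or held beyond 21 days | Not named |
| Bronchospasm, related, grade 3+ | Discontinue | As above | Not named |
| Bronchospasm, grade 1-2 | Discontinue | No stated action | Not named |
| Allergy or hypersensitivity, related, grade 3-4 | Discontinue | As for ARDS; not excepted in 13.4.2 | Off study, no grade given |

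**Step 4: count.** 9.1.1.3 names 3 permanent-stop events. Section 13.4 names 0 of them and 13.5 names 1 (allergy). That leaves 3 - 1 = 2, ARDS and bronchospasm, without a named stop in either section.

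**Step 5: remaining schedule.** The planned total is 17 doses. After a reaction to the loading dose, 17 - 1 = 16 doses would remain. This is the length of the schedule still open to the patient, not an estimate of harm.

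**Step 6: is the difference one of substance?** Within 9.1.1.3 itself, the events after which dosing may resume are kept apart from those that end it. Under 13.4, ARDS and grade 3+ bronchospasm fall among events after which dosing may resume. The two rules therefore give different instructions for the same patient.

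**The case against.** **9.1.1.3 may still apply.** It speaks of events at any time during the study. However, that phrase belongs to the sentence on toxicity judged unmanageable by patient and physician, not to the sentence with the permanent stops. Its place under Phase 1, and the pointer in 9.1.2, also weigh against this reading.

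**Related grade 3+ events are not unregulated.** This is correct. A reader might infer from the missing stops that ARDS and bronchospasm are left wholly to the investigator's discretion in Phase 2. The documents do not support that: 13.4 imposes a mandatory hold, fixed restart criteria and a 21-day stop. Discretion (through 13.5 or 13.7.1) decides only whether to refuse a permitted restart, and what to do about grade 1-2 bronchospasm.

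**13.4.2 permits re-treatment; it does not order it.** This also stands. In addition, bronchospasm judged allergic could be taken off study under 13.5 at any grade. That depends on how the event is classified and does not help for ARDS.

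**Allergy is covered.** Largely so. 13.5 says these subjects come off study and points to 13.7.2 for follow-up. A reader might infer that the missing grade sweeps in the local histamine reactions that 5.6.2 expects in 10-30% of subjects. That reading is strained: 5.6.2 lists them as expected effects resolving within a couple of hours, and the injection-site rule in 13.4.1 and 13.4.2 can largely cover them.

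**Other safeguards exist and no signal is shown.** Both are true. Section 9.1.3 requires heart rate, oxygen saturation and blood pressure after every injection, and 14.3 provides DSMB review at least twice a year and ad hoc. ARDS and bronchospasm are not in the 5.6.2 risk list, and the two related grade 3+ events in Phase 1 were tachycardia and hypotension. The Phase 2 list was evidently revised, since it adds injection-site and QTc rules, so the omission could be deliberate; the documents give no reason either way. None of this removes the conflict between the two sections.

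**Conclusion.** The inconsistency is real and minor. In Phase 2, 13.4 as written permits re-challenge after a related grade 3+ ARDS or bronchospasm that resolves to grade 1 or baseline within 21 days, where 9.1.1.3 forbids it. It states no action for grade 1-2 bronchospasm. For grade 3-4 hypersensitivity the problem is only that 13.4.2 has no exception while 13.5 has an ungraded off-study rule.

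This rests on reading 9.1.1.3 as a Phase 1 rule and 13.4 as the complete Phase 2 set, which the section structure and 9.1.2 support. How often these events occur cannot be estimated from the documents; it is probably low. A reader might infer that patients are still at risk. SAP Section 4 describes BMX-001 administration in the past tense, and SAP 8.3.1 places the first interim analysis in December 2021, so Arm A dosing is probably complete and rewording would now protect few patients or none. No endpoint, analysis population, error rate or power figure changes.

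**What to change.** **If any Arm A dosing remains:**
- Add grade 3-4 allergic reaction or hypersensitivity, ARDS, and bronchospasm of any grade to 13.4.3 as immediate permanent discontinuation of BMX-001.
- Exclude these events from re-treatment in 13.4.2.
- State in 13.5 the grade of allergic reaction meant, matching 13.4.3.

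The cost is a few sentences and a letter to sites, with no extra visits, tests or patients.

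**If dosing is complete:** report how each such event was handled (stopped, held, restarted or off study). The sources are already planned: the withdrawal list with reasons and the total BMX-001 dose (SAP 7), SAE narratives (SAP 11.2.2), the listing of all AEs (SAP 11.2.4) and the exposure table (SAP 19). Use Arm A patients in the Safety Population who received at least one BMX-001 dose. The Treated Population requires at least 6 weeks or 13 doses, so it would miss a patient stopped early. The cost is one short table, or a sentence if there were no such events.
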